### **Analysis of exposure-adjusted incidence rate**

If the cumulative duration of treatment exposure is imbalanced between dupilumab and placebo, then the number of participants with at least one TEAE per 100 participant-years will be provided for the below summaries:

- Overview of adverse events profile
- TEAE by primary SOC and PT
- Common TEAE ( $\geq 5\%$  in any group) by primary SOC and PT
- Treatment-emergent SAE by primary SOC and PT
- TEAE leading to permanent intervention discontinuation by primary SOC and PT
- Treatment-emergent AESI and other selected AE grouping events by category and PT

For participants with an event, the number of participant-years will be calculated up to the first event; for participants without an event, the number of participant-years will correspond to the length of the treatment-emergent period.

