### Investigational medicinal product(s)

The IMP is administered every  $14 \pm 3$  days (q2w) during the treatment period (with the last IMP administration at Week 22-50).

During study visits, the IMP is administered on sites after all procedures. For the doses that are not scheduled to be given at the study site, home administration of IMP is allowed after appropriate training of the participant or caregiver). Investigator or delegate will prepare and inject the first dose of IMP at Visit 2, in front of the participant (or caregiver). The participant (or caregiver) will prepare and inject the IMP under the supervision of the Investigator or delegate at Visit 3. The training must be documented in the participant's study file. In case of emergency (eg, natural disaster, pandemic, etc) different training ways (eg, training remotely with instruction provided by phone, etc) can be performed (and will be documented in the participant's study file).

If the participant (or caregiver) is unable or unwilling to prepare and inject IMP, injections can be performed at the study site by way of unscheduled visits; or arrangements can be made for qualified site personnel and/or health care professionals (eg, visiting nurse service) to administer IMP at participant's home.

In case of emergency (eg, natural disaster, pandemic, etc), IMP may be supplied from the site to the participant via a Sponsor-approved courier company where allowed by local regulations and approved by the participant. When the participant has a study visit, the IMP will be administered after clinical procedures and blood collection are performed. Participants should be monitored for at least 30 minutes following injection. The monitoring period may be extended as per country-specific or local site-specific requirements.

The participant/parent/legally authorized representative/caregiver should be trained by the site staff to recognize potential signs and symptoms of hypersensitivity reaction in order to self-monitor/monitor at home for at least 30 minutes (or longer per country-specific or local site-specific requirements) following injection. In case of hypersensitivity symptoms, the participant should contact healthcare provider/emergency.

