## **7.2 PARTICIPANT DISCONTINUATION/WITHDRAWAL FROM THE STUDY**

- A participant may withdraw from the study at any time at his/her own request or if his/her caregiver(s) or may be withdrawn at any time at the discretion of the Investigator for safety, behavioral, compliance, or administrative reasons. This is expected to be uncommon.
- At the time of discontinuing from the study, if possible, an early follow-up/EOS Visit should be conducted, as shown in the SoA ([Section 1.3](#)).
- The participant will be permanently discontinued both from the study intervention and from the study at that time.
- If the participant withdraws consent for the disclosure of future information, the Sponsor may retain and continue to use any data collected before such a withdrawal of consent.
- If a participant withdraws from the study, he/she may request destruction of any samples taken and not tested; and the Investigator must document this in the site study records.
- All study withdrawals should be recorded by the Investigator in the appropriate screens of the eCRF and in the participant's medical records. In the medical record, at least the date of the withdrawal and the reason should be documented.
- In addition, a participant may withdraw his/her consent to stop participating in the study. A participant's decision to discontinue intervention should be distinguished from withdrawal of consent for follow-up visits and from withdrawal of consent for non-participant contact follow-up, eg, medical record checks. The site should document any case of withdrawal of consent.

Participants who have withdrawn from the study cannot be rerandomized (treated) in the study. Their inclusion and intervention numbers must not be reused.

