#### *Observation period*

The observation period will be divided into 4 segments:

- The **pre-treatment period** is defined as the period up to the first IMP administration.
- The **treatment-emergent (TE) period** is defined as the period from the first IMP administration to the last IMP administration + 98 days. The treatment-emergent period includes the following 2 periods:
  - The **on-treatment period** is defined as the period from the first IMP administration to the last administration of the IMP + 14 days
  - The **residual treatment period** is defined as the period from the end of the on-treatment period to the end of the treatment-emergent period.
- The **post-treatment period** is defined as the period after the end of the treatment-emergent period.

The on-study observation period is defined as the time from the first IMP until the end of the study defined as the last scheduled visit for those who completed the study and the end-of-study date

collected on electronic case report form (e-CRF) page “Completion of End of Study/Follow-up” for those who did not complete the study. If death is the end-of-study reason, date of death will be used.

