- For each AESI and other selected AE groupings,
  - Number (%) of participants with any TEAE
  - Number (%) of participants with any serious AE (regardless of treatment-emergent status)
  - Number (%) of participants with any treatment-emergent serious AE
  - Number (%) of participants with any AE leading to death
  - Number (%) of participants with any TEAE leading to permanent study intervention discontinuation
  - Number (%) of participants with any TEAE related to IMP reported by investigator
  - Number (%) of participants with any TEAE by maximum intensity, corrective treatment, and final outcome
  - Number (%) of participants with any TEAE adjusted by the exposure duration
- Number (%) of participants with injection site reactions by the related injection.
- Number (%) of participants with different number of injection site reactions.

In addition, AESIs reported by the investigator in eCRF will be summarized separately.

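### Exposure-adjusted adverse event rates count time after early study exit, because event-free person-time runs to last dose + 98 days with no cut at end of study or death

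*SAP*

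**What the plan says.** SAP 3.6.2, under the exposure-adjusted incidence rate, plans rates per 100 participant-years for the adverse event overview, TEAEs, common TEAEs, serious TEAEs, TEAEs leading to discontinuation, and AESIs with the other selected groupings. They are conditional: "If the cumulative duration of treatment exposure is imbalanced between dupilumab and placebo". No threshold for imbalance is set.

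The denominator has two parts. "For participants with an event, the number of participant-years will be calculated up to the first event"; and "for participants without an event, the number of participant-years will correspond to the length of the treatment-emergent period". SAP 3.1 (Observation period) says that the treatment-emergent period "is defined as the period from the first IMP administration to the last IMP administration + 98 days".

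The same part of SAP 3.1 defines an on-study period with a different end: "the end of the study defined as the last scheduled visit for those who completed the study and the end-of-study date" from the eCRF for those who did not complete, or the date of death where that applies. The rate calculation does not use it.

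On leaving the study, Protocol 7.2 says: "The participant will be permanently discontinued both from the study intervention and from the study at that time". Protocol 7.3 treats a participant who stays unreachable as withdrawn. Protocol 8.3.1 does not oblige investigators to seek adverse events actively once participation has ended.

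Among the AESI summaries listed after Table 6 in SAP 3.6.2 is "Number (%) of participants with any TEAE adjusted by the exposure duration". That row has no stated imbalance condition and no person-time definition of its own.

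**The concern.** A person-time rate needs a denominator made of time in which an event could have been counted. Tying the end of that time to the last dose alone breaks this for one group: event-free participants who leave the study less than 98 days after their last dose. Their remaining days enter the denominator although routine collection has stopped. Days after a death would be counted as well.

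The error goes one way, because a larger denominator lowers the rate. If both arms lose participants, both rates are understated, and the arm with more early exits is understated more. It is the difference between arms that distorts the comparison. The tables exist to correct for unequal exposure, and early study exits are one way in which exposure becomes unequal, so the correction can be least reliable when it is called on.

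**Working it through.** **The plan's own figure.** The 98 days equal one 14-day dosing interval plus the 12-week follow-up: 14 + 84 = 98. Protocol 6.1 describes dosing "with the last IMP administration at Week 22-50". Week 22 is day 154, and 154 + 98 = 252 days = Week 36. Week 50 is day 350, and 350 + 98 = 448 days = Week 64. Both match the end-of-study visit in the schedule of activities (Week 36 to Week 64). The rule therefore fits completers and can fail only for early leavers.

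**Who is affected.**
- Completers: person-time ends at the scheduled last visit. No unobserved time.
- Participants who stop drug but remain in the study: Protocol 7.1.1 keeps them in follow-up, so the 98 days are normally observed.
- Participants who leave the study *g* days after the last dose, with *g* below 98, and have had no event: 98 − *g* unobserved days each.

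**One participant.** Last dose at Week 10 (day 70), exit at day 84: observed time is 84 days, and the SAP rule counts 70 + 98 = 168 days.

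**One arm.** From the documents: about 35 per arm, last planned dose Week 22 to Week 50, 98-day tail. Assumed, because the documents do not give them: study withdrawal of 10% or 20%, leavers' last dose at Week 10, exit 0 or 14 days later (98 or 84 unobserved days each), and events rare enough that truncation at first event can be ignored.

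Denominator under the SAP rule = completers × (252 or 448) + leavers × 168. Unobserved time = leavers × (98 or 84).

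| Withdrawal | Completers' last dose | SAP denominator (days) | Unobserved, exit at last dose | Unobserved, exit 14 days later |
|---|---|---|---|---|
| 10% | Week 22 | 31.5×252 + 3.5×168 = 8,526 | 343 (4.0%) | 294 (3.4%) |
| 10% | Week 50 | 31.5×448 + 3.5×168 = 14,700 | 343 (2.3%) | 294 (2.0%) |
| 20% | Week 22 | 28×252 + 7×168 = 8,232 | 686 (8.3%) | 588 (7.1%) |
| 20% | Week 50 | 28×448 + 7×168 = 13,720 | 686 (5.0%) | 588 (4.3%) |

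**Between arms.** With equal true rates, 20% withdrawal in one arm and none in the other, the apparent rate ratio (no-loss arm over the other) is the SAP denominator divided by observed time in the arm with losses:
- Week 22 completers: 8,232/7,546 = 1.09, or 8,232/7,644 = 1.08 with exit 14 days later.
- Week 50 completers: 13,720/13,034 = 1.05, or 13,720/13,132 = 1.04.

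**Commoner events.** A constant-hazard model that does truncate at the first event (completers at 252 days, leavers' last dose at day 28 to 126, exit 0 to 14 days later, event risk 5% to 60%) gives an understatement of about 3-5.5% at 10% withdrawal and 6-11% at 20%.

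**As a reported rate.** Let 4 of 35 leave at day 84 after a last dose at day 70, the rest contribute 252 days, and ignore truncation. Observed time is 31×252 + 4×84 = 8,148 days = 22.31 participant-years. The SAP rule gives 31×252 + 4×168 = 8,484 days = 23.23. With 5 events the rates are 22.4 and 21.5 per 100 participant-years.

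**The case against.** **The period may be cut implicitly.** SAP 3.1 introduces the treatment-emergent period as one segment of the observation period, and a segment of observation could be read as ending when observation ends. But the definition itself names two dosing dates and a fixed 98 days, and the neighbouring on-study definition shows that the end-of-study date was written in where it was wanted. The explicit wording governs.

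**The effect is small and the tables are supplementary.** This stands. SAP 3.6 describes the safety analysis as essentially descriptive with no testing. An exact Poisson 95% interval on 5 events runs from about 1.6 to 11.7, or roughly 7 to 52 per 100 participant-years on 22.31 participant-years, so a shift of about 4% is well inside the noise. Protocol 7.2 expects study withdrawal to be uncommon.

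**Stronger readings that the documents do not support.**
- A reader might infer that the secondary safety endpoint is biased. It is incidence, tabulated as number (%) of participants, and uses no person-time.
- A reader might infer that nothing can be recorded after exit. Protocol 8.3.1 still requires prompt notification of an SAE judged reasonably related if the investigator learns of one. Collection is reduced, not abolished.
- A reader might count treatment discontinuation as loss. Those participants stay under follow-up.
- A reader might take the plan's 10% dropout as forecast study withdrawal in the safety population. It belongs to the precision calculation for the Week 24 LMK endpoint in the ≥300 cells/mm³ group, and serves here only as an illustrative value.

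**Conclusion.** The denominator is wrong as written for event-free participants who leave the study less than 98 days after their last dose. The direction is certain: exposure-adjusted rates are too low, and more so in the arm with more early study exits. Which arm that would be cannot be said from the documents.

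The size is an assumption range. Over the cases in the table it is about 2.0-4.0% of an arm's denominator at 10% study withdrawal and 4.3-8.3% at 20%. A contrast of 20% against 0%, which nothing in the documents predicts, would shift the rate ratio by about 4-9%. Exit later than 14 days after the last dose would shrink these figures.

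This is a modest, systematic and avoidable error in conditional descriptive tables. It does not threaten the secondary safety endpoint's number (%) tables. It is worth correcting because the rates will be read at face value and the correction is nearly free.

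**What to change.** In SAP 3.6.2, state that for participants without an event, person-time runs from first IMP to the earliest of last IMP + 98 days, the end-of-study date already defined in SAP 3.1, and death. State also that the AESI and other selected grouping rows adjusted for exposure duration use the same person-time.

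The cost is a sentence or two in the SAP and a minimum of three dates in the program. All three dates are already collected. No new data and no change to trial conduct are needed, and completers' person-time stays essentially the same.

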### **3.6.3 Additional safety assessments**

#### ***3.6.3.1 Laboratory variables and vital signs***

The following laboratory and vital signs variables will be analyzed. They will be converted into standard international units.

- Hematology:
  - Red blood cells and platelets and coagulation: hemoglobin, hematocrit, red blood cell count, platelet count
  - White blood cells: white blood cell count, neutrophils, lymphocytes, monocytes, basophils, eosinophils
- Clinical chemistry:
  - Metabolism: glucose, total cholesterol, total protein, albumin
  - Electrolytes: sodium, potassium, chloride, bicarbonate
  - Renal function: creatinine, creatinine clearance, blood urea nitrogen, uric acid
  - Liver function: alanine aminotransferase, aspartate aminotransferase, alkaline phosphatase, lactate dehydrogenase, total bilirubin
  - Pregnancy test: Urine pregnancy test
- Vital signs: heart rate, systolic and diastolic blood pressure, weight, respiratory rate, temperature, BMI

Data below the lower limit of quantification (LLOQ) will be replaced by half of the LLOQ, data above the upper limit of quantification (ULOQ) will be replaced by ULOQ value.

## **Quantitative analyses**

For laboratory and vital signs variables above, descriptive statistics for results and changes from baseline will be provided for each analysis window, the last value and the worst value during the on-treatment period. These analyses will be performed using central measurements only for laboratory variables.

For all parameters, mean changes from baseline with the corresponding standard error will be plotted over time.

## **Analyses according to PCSA**

Potentially clinically significant abnormality (PCSA) analyses will be performed based on the PCSA list currently in effect at Sanofi at the time of the database lock. For parameters for which no PCSA criteria are defined, similar analyses will be done using the normal range, if applicable.

Analyses according to PCSA will be performed based on the worst value during the treatment-emergent period, using all measurements (either local or central, either scheduled, nonscheduled or repeated).

For laboratory and vital signs variables above, the incidence of participants with at least one PCSA during the treatment-emergent period will be summarized regardless of the baseline level and according to the following baseline status categories:

- Normal/missing
- Abnormal according to PCSA criterion or criteria

## ***Additional analyses for drug-induced liver injury***

The following additional analyses will be performed for drug-induced liver injury:

- Time to onset of the initial alanine aminotransferase (ALT) or aspartate aminotransferase (AST) elevation ( $>3 \times \text{ULN}$ ) and total bilirubin elevation ( $>2 \times \text{ULN}$ ) during the treatment-emergent period will be analyzed using Kaplan-Meier method.
- A graph of the distribution of peak values of ALT versus peak values of total bilirubin during the treatment-emergent period will be provided.
- For each liver function test (eg, ALT), participants having experienced a PCSA (eg, ALT  $>5 \text{ ULN}$ ) will be summarized using the following categories: Returned to baseline PCSA status (or returned to value  $\leq \text{ULN}$  in case of missing baseline) before last IMP dose, Returned to baseline PCSA status after last IMP dose, Never returned to baseline PCSA status, No assessment after elevation. This summary will be performed by categories of elevation (ALT  $>3, >5, >10, >20 \text{ ULN}$ ).

## 3.7 OTHER ANALYSES

### 3.7.1 Other variables and/or parameters

#### 3.7.1.1 *PK analyses*

Predose serum dupilumab concentrations at Visit 2 (Day 1), dupilumab trough levels at Week 12, Week 24, Week 52 and posttreatment serum dupilumab at the End of Study (EOS) visit will be provided. Given the variable treatment period, the EOS visit may be between 36 to 64 weeks.

Serum concentrations of SAR231893 (REGN668) will be summarized in the PK population using arithmetic and geometric means, SD, standard error of the mean (SEM), coefficient of variation (CV), minimum, median and maximum per sampling time. If date and/or time of the drug injection and/or sampling is missing, then the concentration will not be taken into account. For drug-treated participants, where concentration values are below the LLOQ, one-half of the LLOQ will be used. Values will be expressed in the tables with no more than three significant figures. For participants in the placebo group, concentration values below the LLOQ will be taken into account with a plasma concentration considered equal to 0.

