**Table 3 - Populations for analyses**

Population	Description
Screened	All participants who sign the informed consent form.
Randomized	The randomized population includes all participants with a treatment kit number allocated and recorded in the IRT database, and regardless of whether the treatment kit was used or not. Participants treated without being randomized will not be considered randomized and will not be included in any efficacy population.
Intent-to-treat (ITT)	All randomized participants analyzed according to the treatment group allocated by randomization regardless if treatment kit is used or not.
ITT with screening blood eosinophil count $\geq 300$ cells/mm $^3$	All randomized participants with screening blood eosinophil count $\geq 300$ cells/mm $^3$ analyzed according to the treatment group allocated by randomization regardless if treatment kit is used or not.
ITT with screening blood eosinophil count $< 300$ cells/mm $^3$	All randomized participants with screening blood eosinophil count $< 300$ cells/mm $^3$ analyzed according to the treatment group allocated by randomization regardless if treatment kit is used or not.
Safety	All participants randomly assigned to study intervention and who take at least 1 dose of study intervention. Participants will be analyzed according to the intervention they actually received. Randomized participants for whom it is unclear whether they took the study medication will be included in the safety population as randomized. For participants who accidentally receive different study intervention from the planned, the actual intervention allocation for as-treated analysis will be the dupilumab group.
Pharmacokinetic (PK)	The PK population includes all participants in the safety population with at least 1 non-missing result for functional dupilumab concentration in serum after the first dose of the study intervention. Participants will be analyzed according to the intervention actually received.
Anti-drug antibody (ADA)	ADA population includes all participants in the safety population who have at least 1 non-missing result in the ADA assay after the first dose of the study intervention. Participants will be analyzed according to the intervention actually received.

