**Table 10 - Time window for efficacy variables**

Analysis visit	Target day	Time windows for							
		LMK /3-D CT	UPSiT, VAS	SNOT-22	Spirometry	ACQ-6	EQ-5D-5L	PGIS, HCRU/P	PGIC
Screening	-28 to -14				<14				
Baseline	1	<1-	<1-	<1-	-14-1-	1-	1-	<1-	
Week 2	15		1*-91						
Week 12	85				1*-126	1*-126		1*-126	1*-126
Week 24	169	1*-266	92-224	1*-224	127-266	127-224	1*-224	127-224	127-224
Week 40	281		225-322	225-322		225-322	225-322	225-322	225-322
Week 52	365	267-d	323-d	323-d	267-d	323-d	323-d	323-d	323-d
EOS*	NA		NA	NA	NA	NA			

d: planned EOT date, EOT: End of Treatment, EOS: End of Study

1-: up to randomization and before 1st dose date/time; 1\*: after randomization or 1st dose date/time

\* Data collected at the EOS visit will not be remapped

For the pharmacokinetics/pharmacodynamics variables summary, the reference date for the derivation of relative days of measurements will be the date of first IMP administration if the participant is treated with study intervention, or the randomization date if the participant is not treated. Pharmacokinetics /pharmacodynamics variables will be summarized by the analysis window defined in **Table 11** for the by visit descriptive analyses. All available values of measurements will be assigned to the appropriate visit window. In the event of multiple measurements of the same test in the same window, the one closest to the targeted visit date will be used for the by-visit summary. If they are at the same number of days away from the target day, the latest one will be used. For procedures planned on Visit 2, if it is done on the same date as the first IMP injection but the performance time is missing, it will belong to the Visit 2 window.

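### The SAP's Week 12, 24 and 52 trough concentrations carry no limit on time since the last dose, so an off-drug sample from a participant who stopped early would be averaged in as a trough

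*SAP*

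**What the plan says.** SAP 3.7.1.1 names four kinds of concentration: predose on Day 1, "dupilumab trough levels at Week 12, Week 24, Week 52", and a post-treatment value at the end-of-study visit. It summarises them by arithmetic and geometric mean, median and other statistics.

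Three rules decide which samples count:

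- **Population (SAP Table 3).** For PK this "includes all participants in the safety population with at least 1 non-missing result for functional dupilumab concentration in serum after the first dose". One post-dose result is enough, whenever it was taken.
- **Exclusion and low values (SAP 3.7.1.1).** The only exclusion is: "If date and/or time of the drug injection and/or sampling is missing, then the concentration will not be taken into account". Low values are kept: "For drug-treated participants, where concentration values are below the LLOQ, one-half of the LLOQ will be used".
- **Windows (SAP 5.4, Appendix 4, text before Table 11).** "All available values of measurements will be assigned to the appropriate visit window". Table 11 sets these for serum dupilumab as after first dose to day 126 (Week 12), days 127 to 266 (Week 24) and after day 266 (Week 52). If a window holds several samples, "the one closest to the targeted visit date will be used for the by-visit summary". Only end-of-study samples are kept out of the remapping.

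SAP 3.1 defines an on-treatment period, "the period from the first IMP administration to the last administration of the IMP + 14 days". SAP 3.7.1.1 does not use it.

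On follow-up, Protocol 7.1.1 and footnote c of the schedule of activities (Protocol 1.3) keep participants who stop treatment in the study and ask them to complete the remaining visits and assessments. The schedule includes concentration sampling.

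**The concern.** With dosing every 14 ± 3 days, a trough is the concentration about two weeks after the previous injection. The label in SAP 3.7.1.1 implies that timing, but the selection rules do not enforce it. A scheduled sample taken one or more months after the last injection satisfies every stated rule and would be tabulated as a trough.

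Serum dupilumab concentration is a secondary endpoint. The by-visit means are its main summary, and the geometric mean is sensitive to a few very low values. The same concentrations feed the planned plots by anti-drug-antibody variables (SAP 3.7.1.2.1), where a low value caused by stopping treatment could be misread as an antibody effect.

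**Working it through.** The plan states no concentration figure, so there is nothing to reproduce. The check has a text part and an illustrative size part.

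**1. Does a sample from a stopped participant reach a trough row?**

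Take the Week 24 visit at day 169, which is 168 days after day 1. Days since last dose = 168 − 7 × (week of last dose).

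| Last dose | Days since last dose at Week 24 | Within Week 24 window (127–266)? |
|---|---|---|
| Week 22 | 168 − 154 = 14 | yes, a true trough |
| Week 20 | 168 − 140 = 28 | yes |
| Week 16 | 168 − 112 = 56 | yes |
| Week 12 | 168 − 84 = 84 | yes |

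The last three are not troughs, yet no rule removes them. A participant who stopped still has a recorded last injection, so the missing-date rule does not apply. A result below quantification stays in at half the limit.

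**2. Early-termination samples.** The closest-to-target rule decides. If the early-termination sample falls on day 141 and the Week 24 visit is attended within ± 3 days of day 169, the distances are 28 days and at most 3. The later sample is used. An early-termination sample is therefore counted only when no other sample in its window lies closer to the target.

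**3. Who is not affected.** Participants who finish treatment as planned between Weeks 24 and 52 have an end-of-treatment sample about 14 days after the last dose, and their end-of-study sample is not remapped.

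**4. Size, under assumptions.** Let *f* be the share of off-drug samples in a row and *r* the ratio of an off-drug concentration to the trough. The documents give neither. Then

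- arithmetic mean factor = 1 − *f*(1 − *r*)
- geometric mean factor = *r*^*f*

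| *f* (assumed) | *r* (assumed) | Arithmetic factor | Geometric factor |
|---|---|---|---|
| 1/35 | 0.1 | 0.974 | 0.936 |
| 1/35 | 0.01 | 0.972 | 0.877 |
| 5% | 0.5 | 0.975 | 0.966 |
| 5% | 0.1 | 0.955 | 0.891 |
| 5% | 0.01 | 0.951 | 0.794 |
| 10% | 0.5 | 0.950 | 0.933 |
| 10% | 0.1 | 0.910 | 0.794 |
| 10% | 0.01 | 0.901 | 0.631 |

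The denominator of 35 is the planned size of the dupilumab arm. For example, 0.1^(1/35) = 0.936, a fall of about 6%, and 0.01^0.10 = 0.631, a fall of about 37%. The arithmetic mean cannot fall by more than *f*. Each off-drug sample shifts the median by at most one rank. The Week 52 row will hold fewer than 35 participants because treatment length varies, so one such sample weighs more there.

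**5. Would the existing on-treatment period serve as the filter?** Not well, for two reasons.

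- Protocol 7.1.2 lets a participant resume after one missed dose. A sample taken just before resumption is about 2 × 14 = 28 days post-dose, yet lies inside the on-treatment period.
- If the Week 22 dose is given 3 days early and the Week 24 visit falls 3 days late, a proper end-of-treatment sample is 14 + 3 + 3 = 20 days post-dose. A cut-off at last dose + 14 days, or + 17 with the dosing window added, would drop it.

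**The case against.** The strongest reply is that the word trough already does the work. SAP 3.7.1.1 separates trough levels from the post-treatment end-of-study value, that value is not remapped, and footnote p of the schedule of activities has treatment-period samples taken before the injection. On this view only a clarifying sentence is missing. It does not settle the matter. Footnote p governs collection, not which results are summarised, and only end-of-study samples are kept out of the windows. Nor can a trough here mean only a sample followed by another dose. Protocol 6.1 puts the last injection at Weeks 22 to 50, so a completer's end-of-treatment sample has no following dose either.

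Other parts of the reply stand. The effect is conditional: it needs a dupilumab participant who stops early, stays in the study and gives a sample that the window rule selects. Protocol 7.1.1 expects permanent discontinuation to be rare. The analysis is descriptive, the median is reported too, and individual concentration plots are planned.

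A reader might also infer four stronger things that the documents do not support:

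- **That the 10% dropout rate in the sample-size section gives the off-drug share.** It is not a treatment-discontinuation rate, and participants who leave the study give no later sample.
- **That the geometric mean could be halved.** This needs 10% of samples at 1/1000 of trough (0.001^0.10 = 0.50). The documents give no concentration, half-life or legible quantification limit to support that ratio.
- **That the SAP restricts all antibody results to the on-treatment period and forgot PK.** The restriction in SAP 3.7.1.2 defines treatment-emergent and treatment-boosted response; by-visit antibody status has no such limit.
- **That exposure will look lower than in other indications.** Protocol 4.3 does rely on similar PK across populations, but the SAP plans no such comparison.

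**Conclusion.** The concern holds in conditional form. Applied as written, the SAP's rules count an off-drug scheduled sample as a trough, and the effect on the mean is downward. Whether it happens depends on at least one dupilumab participant stopping early and still being sampled, which the protocol's follow-up makes possible but does not make certain.

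The size is illustrative only. The geometric mean falls by about 6% to 12% for one sample in 35 at 1/10 to 1/100 of trough, and by about 3% to 37% for an assumed 5% to 10% share at 1/2 to 1/100. With that same share, the arithmetic mean falls by about 2.5% to 10%. The median is much less affected. Both *f* and *r* are assumptions. The primary endpoint is untouched. The point deserves correction before database lock because a secondary endpoint would otherwise carry a label that its selection rule does not honour.

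**What to change.** Add one sentence to SAP 3.7.1.1: a sample enters the Week 12, 24 or 52 trough summary only if the time since the immediately preceding IMP dose is consistent with the two-week interval plus the protocol's dosing and visit windows (about 14 days, up to about 20). List or summarise all other post-dose samples separately, as off-treatment or post-missed-dose concentrations. Apply this rule before the closest-to-target selection, so that an ineligible sample cannot displace an eligible one in the same window.

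Time since the preceding dose is a better criterion than the on-treatment period, because it also catches a sample after a single missed dose and keeps valid end-of-treatment samples at the edge of the windows.

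The cost is one sentence and one program filter, using the injection and sampling dates that the SAP already requires. The trough rows will hold slightly fewer samples per visit. No data are lost, since the excluded values are still reported.
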